233	monitored blood glucose (SMBG) readings and self-adjustment of insulin doses				
234	according to protocol.				
235	10. Subject must be willing to perform 8 BG Fingersticks during flights.				
236	11. Subject must be able to read and understand English.				
237	12. In the Investigator's opinion, the subject must be able to follow the instructions				
238	provided to him/her by the study staff and perform all study tasks as specified by				
239	the protocol.				
240	13. At the time of enrollment subject must be available and willing to travel on the				
241	specified dates set up per protocol.				
242	14. Subject must be willing and able to provide written signed and dated informed				
243	consent.				
244					
245					

246	EXCLU	JSION CRITERIA
247		
248	1. (	Current use of an insulin pump.
249	2. 1	Use within the last 3 months prior to enrollment visit 1 of any glucose-lowering
250	(	drug other than insulin.
251	3. ]	Initiation or significant change of any systemic treatment which, in the
252	i	investigator's opinion, could interfere with glucose metabolism, such as systemic
253	(	corticosteroids, beta-blockers or monoamine oxidase inhibitors (inhaled
254	(	corticosteroids allowed).
255	4. ]	Proliferative retinopathy or maculopathy requiring treatment, according to the
256	i	investigator.
257	5. ]	Pregnancy, breast-feeding, the intention of becoming pregnant or not using
258	ä	adequate contraceptive measures.
259	6	Any clinically significant disease or disorder, which in the investigator's opinion
260	(	could interfere with the results of the trial.
261	7. ]	Mental incapacity, psychiatric disorder, unwillingness or language barriers
262	1	precluding adequate understanding or cooperation, including subjects not able to
263	1	read or write, and known or suspected abuse of alcohol, narcotics, or illicit drugs.
264	8. ]	Known or suspected allergy to any of the trial products or related products.
265	9. ]	Receipt of any investigational drug or participation in other trials within 1 month
266	1	prior to Visit 1.
267	10.1	Use of melatonin or sleeping aids for sleep during the travel portion of the study.
268	11. 9	Subject is currently participating in another clinical trial.
269	12. 9	Subject is unsuitable for participation due to any other cause as determined by the
270	]	Investigator.
271		
272	WITHD	DRAWAL CRITERIA
273		
274	Pregnan	icy or intention of becoming pregnant
275	Unable	to participate in the flights
276	Unable	to wear the continuous glucose monitoring device
277	New on	set of serious inter-current illness as assessed by the investigator
278	Subjects	s will be replaced if they withdraw or become ineligible by the research staff from
279	the data	base of eligible participants.
280		
281		

#### 282 SUMMARY PROTOCOL

284

285 \*East coast city can be EWR (Newark) or JFK (John F. Kennedy)

286

287 Randomization will be to begin with either **Glargine or Degludec**. Subsequently

288 participants will switch basal insulin (i.e. from **Glargine** to **Degludec** or from **Degludec** 

to **Glargine**). The direction of travel will be the same direction each time.

### 290 OVERVIEW OF VISIT PROCEDURES

291

Screen	Visit #1	Visit #2	Visit #3	Visit #4	Visit #5	Visit #6	Visit #7
SDRI	SDRI	SDRI or Phone	SDRI or Phone	Travel West to East	EWR/JFK post- flight	Travel East to West	HNL Post-Flight
Consent	Randomize	Optimize Basal	Optimize Basal Completion	HNL to EWR/JFK	Primary End Point Data Collection	EWR/JFK to HNL	Primary End Point Data Collection
	Time = 0	Wk 2 ±3 days	Wk 2-Wk 4 ±3 days	Wk 4 ±7 days	Up to 72 hours	Wk 5 ±3 days	Up to 72 hours
Break	Visit #8	Visit #9	Visit #10	Visit #11	Visit #12	Visit #13	Visit #14
	SDRI	SDRI or Phone	SDRI or Phone	Travel West to East	EWR/JFK post- flight	Travel East to West	HNL post-flight
2 weeks	Cross-over Basal insulin	Optimize Basal	Optimize Basal Completion	HNL to EWR/JFK	Primary End Point Data Collection	EWR/JFK to HNL	Primary End Point Data Collection
	Wk 8 ±3 days	Wk 10 ±3 days	Wk 10-Wk 12 ±3 days	Wk 12 ±7 days	Up to 72 hours	Wk 13 ±3 days	Up to 72 hours

292 293

### \*East coast city can be EWR (Newark) or JFK (John F. Kennedy)

294
-----

Screening Visit: Subjects that meet the eligibility criteria and have signed the informed
 consent will continue to the screening visit which will be performed at SDRI
 (www.sansum.org). The following screening assessments will be completed at baseline
 (pre-randomization):

299

315

- 300 Signed and dated informed consent • • HbA1c assessment either via fingerstick and DCA2000 or equivalent NGSP-301 302 certified point-of-care method, or by local laboratory Inclusion and exclusion criteria 303 • 304 Demographics (date of birth, gender, race and ethnicity) • 305 Medical history • 306 Substance use history (drinking, smoking, and drug habits) • • Concomitant medications 307 Physical examination 308 • 309 • Weight and height 310 • Vital signs will be tested including oral temperature, blood pressure and pulse 311 Urine pregnancy test for all premenopausal women who are not surgically sterile •
- Blood draw for routine blood count, HbA1c, and chemistry panel (values within 3 months prior to enrollment acceptable).
- Hypoglycemia unawareness Gold score (23).
  - Fear of hypoglycemia scale (HFS II) (18).
- Hypoglycemic Confidence Scale (28).

# 318 Subject randomization - Visit #1. Subjects who meet all eligibility criteria, have signed

- 319 the informed consent and completed all screening assessments will continue to
- 320 randomization. Screening and Visit #1 may occur on the same day. A subject will be

- 321 considered enrolled in the study after signing the informed consent. After the study team
- 322 confirms enrollment, the subject will be assigned a unique subject identification number
- 323 which will be used to identify the subject throughout the study and will be used for all
- source documents., At this visit travel plans will be also discussed and booked includingground transportation, flights, hotels and meals.
- 326

327 If for any reason a subject is determined to no longer be eligible for the study after

enrollment but prior to the start of the travel phase of the study, the subject will be considered ineligible to continue and will be exited from the study. No additional study assessments will be required to be completed. The reason for study exit will be clearly documented on the corresponding (eCRF). If an enrolled subject must withdraw or fails to complete the study, the subject will be replaced to ensure at least 25 evaluable

- 333
- 334

Randomization - Visit #1. In Visit 1, subjects will be randomized to either starting
 Degludec or Glargine insulin and begin using this insulin according to the label insert and

337 full prescribing information

subjects.

- 338 (https://www.accessdata.fda.gov/drugsatfda\_docs/label/2015/203314lbl.pdf and
- 339 https://www.accessdata.fda.gov/drugsatfda\_docs/label/2009/021081s034lbl.pdf). For the
- 340 purpose of basal insulin optimization we will use CGM data. Subjects who do not
- 341 currently use CGM will be fitted with a blinded CGM system, the Abbott FreeStyle Libre
- 342 Pro (Abbott Laboratories, Abbott Park, IL). Subjects who are current CGM users may
- continue to use their personal CGM systems for the duration of the study. When
  necessary, clinical study staff will train subjects on inserting and using the study CGM
  devices. The investigator will use clinical judgment to confirm that subjects are suitably
  trained on the safe use of CGMs. Subjects will also be given a study glucometer and
  strips. Study staff will ensure that the study meters and strips pass quality control testing
- and the subject is adequately trained on the use of the study meters as per themanufacturer's instructions.
- 349 350

351 Visits for Basal Optimization – Visits #2 and #3. Once the randomization phase has 352 been initiated, the subject will be sent home and CGM data collection will be ongoing for 353 the purpose of basal and meal-time insulin optimization. Over the next (up to 4) weeks 354 clinical staff will review the dose of basal insulin and make necessary adjustments based 355 on the CGM values at least once a week. Subjects will perform up to 4 fingerstick (FS) 356 blood glucose (BG) measurements with the study meter. The investigator will use clinical 357 judgment to adjust the basal rate, insulin to carbohydrate ratio, and correction factor to 358 ensure subject safety prior to continuing the study. The next visits for basal optimization 359 visits may be conducted remotely via telephone at the subject's preference and investigator's discretion. If any visits are planned to be conducted via telephone, the 360 361 subject will need to be able to upload their CGM data for the investigator to review 362 remotely. At each visit the investigator will re-assess glycemic control. If the investigator determines that it is unsafe for the subject to continue into the travel phase of the study, 363 the subject will not be allowed to continue in the study, and the reason for study exit will 364 365 be documented on the corresponding source document.

368 to 72 hours in Newark or New York (Visit #5), return flight from EWR (or JFK) to 369 HNL (visit #6) and 48 hours in Honolulu (visit #7). Subjects originating in Santa 370 Barbara will travel to Honolulu and spend up to 2 days adjusting. At this point subjects 371 will begin their trip to the New York area. Subjects will base their travel plans at this 372 stage according to routine advice from their clinicians and from 373 www.diabetestravel.org. During travel U100 Glargine and Degludec and rapid acting 374 insulin will be maintained in cool storage  $(36^{\circ}F - 46^{\circ}F [2^{\circ}C - 8^{\circ}C])$  until first use using 375 a proprietary travel storage pack (e.g. Frio Cooling Pack). Once open for use insulins can 376 be used for up to 28 days. During this time they can be safely kept at room temperature 377 up to 86°F (30°C). The sponsor-investigator will ensure the availability of proper storage 378 conditions. During each flight, blood glucose meters and strips and continuous glucose 379 monitoring devices will be taken in hand luggage. All doses of insulin (basal and rapid 380 acting) and time of insulin injections will be recorded in the subject's travel diary as well 381 as sleep and meals. Subjects will perform at least 8 FS BGs during the flight. Subjects 382 who regularly use CGMs may continue their personal CGM systems. 383 384 For each flight the relevant basal insulin will be adjusted as described below. The 385 following secondary end-point measurements will be taken starting immediately before a 386 flight, during the flight, immediately after the flight, and after 48 hours at the destination 387 and immediately before the beginning of each flight: 388 389 Salivary cortisol and melatonin 390 Liverpool Jet-Lag Questionnaire. 391 Sleep and Activity (ActiGraph wGT3X-BT activity monitor) (ActiGraph, Pensacola, FL) 392 Interstitial glucose (CGM) Abbott FreeStyle Libre Pro. 393 Fingerstick blood sugar readings, approximately 8 times a day 394 395 **Crossover.** The return to home will be followed by a 2 week period where the subject 396 will return to their original insulin regimen and recover from long-haul travel. Study 397 insulin will not be provided during this time. 398 399 Visits #8 to #14. After 2 weeks, subjects will start the alternative basal insulin (Glargine 400 U100 to Degludec or Degludec to Glargine U100) and the protocol outlined above 401 repeated with the same direction of travel on the new basal insulin (Figure 3). The above 402 measurements will be repeated as before. 403 404 Visit #15 will be a final visit to return equipment and complete documentation. At time 405 of study completion, the corresponding source document will be completed with the date 406 of study exit. Any new or ongoing adverse events will also be documented. A summary 407 letter will be provided for each subject to inform their usual health care provider. 408 409 410 BASAL INSULIN ADJUSTMENTS FOR TRAVEL 411

Travel to Newark (EWR) or New York (JFK) from Honolulu (HNL) (Visit #4), up

412	For subjects taking long acting basal insulin by injection, travel requires a 4% adjustment
413	to the insulin dose for each time zone traversed (1 hour is 4% of the 24 hour day) (24). To
414	avoid any confounding from the direction of travel, both journeys will be identical for
415	each basal insulin, i.e. beginning in Honolulu. With Degludec as the basal insulin,
416	subjects will take this the next day after arriving at their destination taking into
417	consideration the change in time at the destination. As shown in clinical trials in T1 and
418	T2 diabetes, Degludec allows for flexibility in the timing of dose administration provided
419	a minimum of 8 h and maximum of 40 hours between injections is ensured
420	(www.ncbi.nlm.nih.gov/pubmed/23393185).
421	
422	With Glargine as the basal insulin, subjects will adjust their basal insulin based on
423	discussion with their specialist diabetes team and with information provided at
424	www.DiabetesTravel.org.
425	
426	Westward travel from Newark (EWR)/or New York (JFK) to Honolulu (HNL)
427	
428	This example uses a current dose of Glargine 20 units at 8 PM. The flight departs at
429	10 AM Eastern Standard Time (EST) and arrives at 3 PM the same day local (Honolulu
430	time -HST). Total travel time is 11 hours.
431	
432	Using the Westward Travel Algorithm (Appendix 1), information on the starting time at
433	departure is recorded along with the last time Glargine should be given - 20 units at
434	8 PM the prior evening. As a rule, if Glargine is due during a flight, only half the usual
435	dose (10 units) should be taken.
436	
437	The subject's watch/clock should still be on departure time (EST) and the half of the
438	normal dose (10 units) is given at 8 PM EST. Immediately after this, the watch/clock
439	should be reset to the destination time. Upon landing in Honolulu, the day is now 'longer'
440	despite 11 hours having passed, as it is 3 PM HST. Since only half the basal insulin was
441	given earlier in the day, the subject should give the remaining 50% dose (10 units) at
442	8 PM HST after landing in Hawaii. The next night, the normal insulin dose (20 units) is
443	given at 8PM HST at the new location. By giving half the dose at 2 different times, the
444	Glargine dose is extended out to cover the longer day to prevent hypoglycemia. Use of a
445	time zone map ( http://www.worldtimezone.com/wtz-pacific24.php ) can help to determine
446	how many time zones are traversed.
447	
448	Eastward travel from Honolulu (HNL) to Newark (EWR)/or New York (JFK)
449	
450	This example uses a current dose of Glargine 20 units at 8 PM. The flight departs at 3
451	PM HST from Honolulu and arrives at 7 AM EST in Newark the next day. Total travel

- 452 time is 10 hours. When traveling east, the day gets shorter, so the basal insulin dose given
- 453 during travel can be adjusted one time using the formula (25) (Appendix 2):

$$\mathit{Travel Dose} = \mathit{Normal Dose} imes \left( 0.9 - rac{\# \mathit{of Time Zones Crossed}}{\mathit{Hours Between Basal Insulin Doses}} 
ight)$$

455 For this journey only a single dosage reduction is needed. After the reduced travel dose is

- 456 given, the subject should resume their normal dosing. For other journeys the number of
- time zones to be crossed can be found at http://www.timeanddate.com/time/map/.
- 458

Here the normal dose (20 units) of **Glargine** is given at 8 PM local time the evening before departure. During the flight at 8 PM HST, 13 units of **Glargine** are given per the formula. After this dose is given, the subject needs to change his/her watch to EST. The next full dose of **Glargine** is due 8 PM EST after arrival, which turns out to be 18 hours after the last dose. This reduced time between doses is why less **Glargine** is given on the flight.

465

466 During each flight subjects will be provided with prepared food containing 15g snacks to 467 be eaten every 3 hours until the appropriate time for a main meal at the destination. These 468 snacks and all meals at each destination will be logged. Larger meals will be covered 469 using the subject's usual insulin: carbohydrate ratio and correction factor relevant to the 470 carbohydrate content of the meal. If the subject's glucose falls outside of the required

ranges during this time period, the CGM sensor will alert and prompt the subject toperform a confirmatory finger stick. If the BG value is confirmed to be outside of the

472 perform a commutatory inger stick. If the BO value is commuted to be outside of the 473 acceptable range, the subject will self-treat according to usual practice, printed

474 information and with the help of study staff traveling with them.

- 475
- 476

Assessments for Safety: As both Degludec and Glargine are approved for use for type 1
diabetes in the United States no additional safety requirements are required beyond usual
clinical care. All subjects will be provided with oral glucose for the prevention of
hypoglycaemia. In addition, subjects may have an experienced staff person with them
during travel and will be in contact with SDRI physicians for any advice or problems that
may arise.

- 483
- 484

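### Followed at the usual evening time, the degludec travel instruction puts the first dose after the eastbound flight at 42-43 h, past the 40 h maximum in the same paragraph

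*Combined protocol and SAP*

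**What the plan says.** The travel-visit text states: "For each flight the relevant basal insulin will be adjusted as described below". That makes Basal Insulin Adjustments for Travel the dosing instruction.

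- **Degludec.** The section says "subjects will take this the next day after arriving at their destination taking into" consideration the change in local time. It adds that trials support flexible timing provided "a minimum of 8 h and maximum of 40 hours between injections is ensured". It gives no clock time, no worked example and no explicit statement about a dose falling due in flight.
- **Glargine.** There is an in-flight rule for the westbound journey (if a dose "is due during a flight, only half the usual" amount is taken) and a worked example in each direction with clock times and doses. Westbound, half the "normal dose (10 units) is given at 8 PM EST". Eastbound, a reduced dose is taken in flight at 8 PM Honolulu time, and the next full dose is "due 8 PM EST after arrival, which turns out to be 18 hours after the last dose".

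Rationale for the Study gives the 8-40 h flexibility as the reason degludec may make long-haul travel easier to plan. Inclusion criterion 4 requires a once-daily basal analogue given in the evening. The primary endpoint covers the first 24 hours after each arrival, starting within 2 hours of arriving.

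**The concern.** A once-daily evening user who reads the degludec sentence will most naturally omit the dose that falls due in flight and resume at the usual clock time, either on arrival day or on the day after. Eastbound, both choices run past the limit stated in the same paragraph. The participants have type 1 diabetes and depend on their basal insulin, and the gap falls within or around the 24-hour primary window.

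The wording also leaves the day open. A dose on the arrival evening lies inside the primary window. A dose on the evening after arrival lies outside it. Two people following the same sentence could therefore take their first post-flight dose a day apart, in the arm whose timing flexibility is the reason for the trial.

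**Working it through.** **Inputs**

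- Usual dose at 8 PM. This is the protocol's example time, written for glargine. It is applied to degludec here as an assumption, in line with the evening-dosing criterion.
- Eastbound: departs at 3 "PM HST from Honolulu and arrives at 7 AM EST in Newark the next day. Total travel" time is 10 hours.
- Westbound: departs at "10 AM Eastern Standard Time (EST) and arrives at 3 PM the same day local (Honolulu" time). Total travel time is 11 hours.
- Offset: 5 or 6 hours (Study Design).
- Last dose at 8 PM local the evening before departure, and none in flight. The degludec sentence implies this but does not state it.

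**Reproducing the plan's own figures.** Eastbound, the interval between the same clock time on consecutive days is 24 minus the offset: 24 - 6 = 18 h, as the glargine example states. The example dose is 20 × (0.9 - 6/24) = 13 units, also as stated. The example therefore uses a 6-hour offset.

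**Eastbound, degludec, no in-flight dose**

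- Landing: 8 PM to 3 PM departure is 19 h, plus a 10 h flight = 29 h. If arrival is held at 7 AM local with a 5-hour offset, it is 30 h.
- Usual time on arrival day: 48 - 6 = **42 h**, or 48 - 5 = **43 h**. The protocol's own figure agrees: 24 + 18 = 42. The result does not depend on 8 PM, because any unchanged clock time gives 48 minus the offset.
- The 40 h limit is 2 h before the usual time (6-hour offset) or 3 h before (5-hour offset): 6 PM or 5 PM local.
- Earliest moment of the day after arrival (midnight, 4 h after 8 PM): 42 + 4 = **46 h**, or 43 + 4 = **47 h**. No clock time that day complies.
- Usual time on the day after arrival: 42 + 24 = 66 h, or 43 + 24 = 67 h.

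**Westbound, degludec, no in-flight dose**

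- Usual time on arrival day: 24 + 6 = **30 h**, or 24 + 5 = **29 h**. Both comply.
- Usual time on the day after arrival: 30 + 24 = **54 h**, or 29 + 24 = **53 h**. Both exceed the limit.

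**Position relative to the primary window (eastbound, 6-hour offset).** The arrival-evening dose falls 42 - 29 = 13 h after landing, inside the window. The next evening's dose falls 66 - 29 = 37 h after landing. The window ends at most 2 + 24 = 26 h after landing, so that dose is outside it.

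**Compliant slot eastbound.** From landing (29 h) to 40 h is 11 h: 7 AM to 6 PM local with a 6-hour offset.

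**The case against.** The strongest reply is that the breach appears only if the participant disregards the 8-40 h proviso in the same paragraph. Nothing tells degludec users to keep their usual clock time, and eastbound there are about 11 compliant hours after landing. This stands: the protocol does not mandate an interval outside the limits. But the proviso is written as a property shown in clinical trials, not as a step for the participant. Nowhere does the text say that the eastbound dose must come 2-3 hours earlier than usual. Westbound, the compliant 29-30 h case needs same-day dosing, which the words about the next day do not clearly give.

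Second, other controls exist. Randomization - Visit #1 requires use according to the label. The travel-visit text refers subjects to their clinicians and the travel website. Assessments for Safety provides contact with study physicians and possibly a travelling staff member. These reduce the risk. Their content is not available here, and neither are Figure 3 and the appendices. The appendices are cited only in the glargine examples, but it cannot be excluded that a figure adds degludec timing.

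Third, flexibility is the property under study and glargine dosing is also individualised, so a fixed rule narrows the intervention. That is a fair cost. It also means a reader should not infer that the degludec regimen is wholly undefined. What is missing is a timing rule that keeps the instruction within its own limit.

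**Conclusion.** The point holds as a conflict between the instruction, followed at the usual evening time, and the 40 h maximum beside it. Eastbound on arrival day the excess is 2-3 h (42-43 h). On the day after arrival it is at least 6-7 h for an 8 PM user. Westbound is compliant on arrival day (29-30 h) and not at the usual time a day later (53-54 h).

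This rests on three assumptions: degludec is taken in the evening, the last dose is the evening before departure with none in flight, and flights resemble the protocol's examples.

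A reader might go further and infer that the protocol orders intervals above 40 h, or that the comparison of time in range is biased. The documents support neither. The 8-40 h condition leaves a compliant route, and nothing in them allows an effect on glucose to be estimated. The sentence should be fixed because it is the operative dosing text and the repair is small.

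**What to change.** Replace the degludec sentence with one rule per direction:

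- **Both directions:** last dose at the usual time on the evening before departure, none in flight.
- **Eastbound:** next dose on arrival day at a fixed time after landing, at least 3 hours before the usual clock time (no later than 5 PM local for an 8 PM user). Return to the usual time the next day.
- **Westbound:** next dose at the usual local evening time on arrival day.

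If the eastbound dose is k hours before the usual clock time, the intervals are 42 - k or 43 - k, then 24 + k. At 5 PM (k = 3) they are 39 or 40 h, then 27 h, which leaves little or no margin. At noon (k = 8) they are 34 or 35 h, then 32 h. An earlier fixed time is therefore safer, and the investigator can choose it.

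Add a worked degludec timeline for each direction showing hours between doses, to match the glargine examples. Summarise actual dose-to-dose intervals by direction, with counts above 40 h and below 8 h.

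The cost is a short rule, two timelines and an update to the participant instructions. Injection times are already recorded in the travel diary, so no new data are needed. The downside is slightly less dosing flexibility for participants.

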531	In addition the secondary end-points will be compared for Glargine and Degludec for
532	specific time blocks to assess the contribution from each basal insulin:
533	A. Between 2200 and 0700 hours the night before each flight
534	B. Between 2200 and 0700 hours for Days 2 and 3 at each destination
535	For the purpose of our primary outcome data CGM data will primarily be obtained from
536	the Abbott FreeStyle Libre Pro system, but in the case of missing data, we will also
537	evaluate any secondary personal CGM data.
538	
539	Sample size for this pilot study is based on recent data indicating that individuals with
540	type I diabetes spend approximately $669\pm208$ minutes between /0-180 mg/dl (26). With
541 542	the criterion for significance set at 0.05, and using a paired t-test analysis, a sample size of 22 subjects will achieve a power of at least $800/$ to detect a difference of $100/$ between
342 542	basel insuling assuming the standard deviation of the difference is <106 minutes (Table
545 511	1 Although Battelino et al (26) reported the standard deviation of the target
544 575	neasurement it did not report the standard deviation of the difference in the
545	measurement, it did not report the standard deviation of the difference in the

- 546 measurements. Since this is unknown, yet needed for the power calculation, an estimate
- 547 was derived using the two treatment groups reported by the Battelino et al (26) using
- 548 Altman (27). This derivation yielded a value of 25.7. It is acknowledged that the two
- 549 treatment groups reported by Battelino et al (26) are different than those investigated in 550 this protocol (and the groups were independent rather than paired), but since similarities
- exist the derived estimate is sufficient for preliminary power calculations. Table 1
- reports that when the standard deviation of the difference is 25, this investigation will
- have over 99% power to detect a difference between the two insulin groups. Since 25 is a
- by low estimate, Table 1 also reports standard deviation estimates up to 110, and reports that
- 555 >80% power is achieved up to 106 but <80% when the standard deviation of the
- 556 difference is >106. Assuming that the standard deviation of the difference in this
- 557 investigation will be  $\leq 106$  minutes is justified given that the value of this standard
- deviation in a previous study (26) is 25.7 which is well below the 106 threshold. In

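### The in-flight CGM alert is stated for every subject, but the only CGM assigned to subjects who do not already use one is a blinded sensor

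*Combined protocol and SAP*

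**What the plan says.** Under Basal Insulin Adjustments for Travel, at the end of the eastward example, the protocol describes what happens if a subject's glucose leaves the required "ranges during this time period, the CGM sensor will alert and prompt the subject". The prompt is to do a confirmatory fingerstick and then self-treat. No type of subject or device is excepted. The same paragraph speaks of help from study staff who are travelling with the subject.

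The device assignments are elsewhere:

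- **Randomization, Visit #1.** Subjects who do not "currently use CGM will be fitted with a blinded CGM system, the Abbott FreeStyle Libre" Pro. Existing users may keep their own systems. The sensor is introduced in the context that for the "purpose of basal insulin optimization we will use CGM data".
- **Travel visits #4 to #7.** The list of measurements made before, during and after each flight includes "Interstitial glucose (CGM) Abbott FreeStyle Libre Pro". Subjects "who regularly use CGMs may continue their personal CGM systems". Separately, "Subjects will perform at least 8 FS BGs during the flight".
- **Statistical Considerations.** Primary outcome data come mainly from "the Abbott FreeStyle Libre Pro system, but in the case of missing data, we will also" "evaluate any secondary personal CGM data".
- **Study Drugs and Materials.** The Libre Pro is again described as blinded. The Auxiliary Supply list includes Dexcom G4 or G6 and FreeStyle Libre systems, without saying who wears them.
- **Management of Hypoglycemia.** A low-glucose CGM alert at 70 mg/dL is one of four triggers for a meter test.
- **Assessments for Safety.** An experienced staff member may accompany subjects; this is not stated as certain.

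**The concern.** The alert sentence reads as a safeguard covering everyone on board. For a group the protocol plans to enrol (Study Design refers to CGM-naïve subjects, and Visit #1 makes an arrangement for them), the assigned device does not appear able to deliver it. An investigator or ethics committee reading only the travel section would believe that every subject is warned of low or high glucose in flight.

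The setting gives this some weight. The Background names hypoglycemia as the commonest problem during a journey and in the first 24 hours after arrival, and it raises the perception of low glucose at altitude as an issue. In the eastward example a glargine dose is taken in flight and the aircraft lands at 7 AM destination time, so subjects may sleep for part of the flight. The eight required fingersticks have no set timing. They could be bunched together, leaving long stretches with neither an alert nor a test.

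**Working it through.** The plan gives no figure for this point, so the check is a comparison of the text followed by simple arithmetic on exposure and test spacing.

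**Step 1: is the Libre Pro worn in flight, or only during basal optimization?** Visit #1 introduces it for optimization. The travel visits list it among the in-flight measurements, and Statistical Considerations makes it the main source of the primary outcome. It is the travel sensor.

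**Step 2: would it alert the subject?** The protocol does not describe its alarm function. It does call the device blinded, in two places. A device that tells its wearer that glucose is out of range is not blinded to that wearer. That it does not alert is therefore an inference from the protocol's own word, not a stated fact.

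**Step 3: does a non-user have a second, alerting CGM?** The travel visits and Statistical Considerations mention only one other source, the subject's personal system, which a non-user does not have. Dexcom appears in inclusion criterion 7 (as an example), in the supply list and in the definition of device-relatedness under Adverse Event Relatedness. None of these assigns it to non-users.

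Steps 1 to 3 together mean that, following the text exactly, the alert does not operate for subjects whose only CGM is the Libre Pro. The 70 mg/dL trigger under Management of Hypoglycemia simply never applies to them. That is not itself a contradiction, because the other triggers there still apply.

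**Step 4: exposure per affected subject.** Inputs: two journeys of two flights each (Study Design); 9 to 10 h eastward (Endpoints); 11 h westward (westward example).

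- Flights: 2 × 2 = 4.
- Low: 2 × 9 + 2 × 11 = 40 h. High: 2 × 10 + 2 × 11 = 42 h.
- If the westward flight may be 10 h (assumption), the low end is 2 × 9 + 2 × 10 = 38 h.
- Required in-flight fingersticks: at least 4 × 8 = 32.

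**Step 5: spacing of the required tests.** Spread evenly, eight tests are 540/8 = 67.5 min apart on a 9 h flight, 600/8 = 75 min on a 10 h flight and 660/8 = 82.5 min on an 11 h flight. The plan does not require even spacing.

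**Step 6: would a simple schedule meet the requirement?** Testing at take-off and every 75 min gives floor(minutes/75) + 1 tests:

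- 9 h: floor(540/75) + 1 = 8
- 10 h: floor(600/75) + 1 = 9, the last falling at landing
- 11 h: floor(660/75) + 1 = 9

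The minimum of eight is met at each length, with at most one extra test per flight.

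**Step 7: how many subjects?** Not stated. The range runs from none to all 25 planned recruits, and could exceed 25 if withdrawn subjects are replaced.

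**The case against.** The best opposing case is that this is a missing assignment sentence and not a failed safeguard. The Institute buys Dexcom systems while existing users may keep their own, so the purchased ones would plausibly go to others. Criterion 7 allows for both kinds of device. Study Design says a month of use gives CGM-naïve subjects familiarity with the system, which fits poorly with a sensor they cannot read. Visit #1 mentions training on study devices in the plural. All this makes an intended alerting device quite possible. It does not remove the gap, because no section says that non-users receive one.

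The second argument is that little depends on the alert. Assessments for Safety does not list it. Subjects still have the eight or more fingersticks, tests prompted by symptoms or staff concern, 15 g snacks every 3 hours, oral glucose and physician contact. Criterion 6 bars hypoglycemia unawareness and recurrent severe hypoglycemia. This argument stands and limits the severity, but it does not make the sentence correct.

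A third objection is that timed tests may wake subjects, and sleep is a secondary endpoint. That is fair. Using the same schedule in both periods balances the disturbance between insulins without removing it.

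**Conclusion.** The point holds as a modest safety correction that should be made before travel begins. The alert is stated without condition, and for subjects whose only CGM is the blinded Libre Pro the protocol provides nothing that would be expected to deliver it. The conclusion assumes that blinded has its ordinary meaning and that non-users receive only what the text assigns to them.

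A reader might infer more than the documents support:

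- **That the alert is proven impossible.** The protocol never describes the Libre Pro's alarms, and a Dexcom may have been meant.
- **That these subjects fly unprotected.** The remaining safeguards are substantial, and the number affected may be zero. The 40 to 42 hours measure flight time, not harm.
- **That the trial's inference is damaged.** Nothing here bears on alpha, sample size, power or the comparison of the two insulins.
- **That subjects flying without staff must have a companion carrying glucagon, or that staff must be on every flight.** The protocol places glucagon with staff and does not address flights in that passage. Such a rule would add resources without resolving any contradiction, and Assessments for Safety asks for nothing beyond usual care. It is not part of this point.

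The mismatch on staff, presumed present in one place and optional in another, is minor by itself.

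**What to change.** 1. In the travel section, limit the alert sentence to subjects wearing an unblinded, alerting CGM. Limit the 70 mg/dL alert trigger under Management of Hypoglycemia in the same way.
2. For subjects with only the Libre Pro, choose one of the following:
   - Spread the eight or more fingersticks already required across the flight, for example at take-off and about every 75 min, identically in both crossover periods.
   - State that these subjects wear one of the listed Dexcom systems in both periods.
3. Make the travel section and Assessments for Safety agree on whether staff travel with subjects.

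Items 1 and 3 cost only wording. The timed schedule needs no new device and adds at most one fingerstick per flight, with some possible disturbance of sleep. The Dexcom option uses a device already on the supply list but needs extra sensors and training for these subjects. The analysis does not change.
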